### **7.13.1 Duration**

Imputation will only be used for analyses of duration endpoints and only in the MITT Population. Duration for subjects who drop out prior to healing will be imputed with a duration of 336 hours (14 days x 24 hours) for the main analyses of duration endpoints in the MITT Population. Hodges-Lehmann technique will be used for estimation and Wilcoxon rank sum tests will be used to compare the groups on duration endpoints in the MITT Population. In addition, subjects who drop out prior to healing will be considered censored in a sensitivity analysis of duration endpoints in the MITT Population and Kaplan-Meier estimation methods will be used with log-rank tests for comparison of the groups.

For analysis of duration in the EE Population, no imputation is required since these are complete cases. Hodges-Lehmann technique will be used for estimation and Wilcoxon rank sum tests will be used to compare the groups on duration endpoints in the EE Population.

### **7.13.2 Prevention of Progression**

For all endpoints on the occurrence of prevention of progression, counts and percentages will be summarized, and chi-square tests, or Fisher's exact test will be used to compare groups, as appropriate. Fisher's exact tests will be used if any of the expected cell counts in the Rx C crosstabulations are less than 5.

### **7.13.3 Area**

For area endpoints, means, medians, standard deviations and ranges will be summarized. T-tests will be used to compare groups if the sizes are approximately normally distributed, or Wilcoxon rank sum tests will be used if the sizes are markedly non-normally distributed.

### **7.13.4 Pain Severity**

For pain severity, counts and percentages will be summarized for all levels of severity, and Cochran-Mantel-Haenszel tests will be used to compare the groups.

### 7.13.5 Analysis Matrix

For all efficacy endpoints the following matrix will be used for analyses:

Endpoint	Popu- lation	Analysis	Description	Methods
Duration	MITT	Main Analysis	Impute duration for subjects who drop out prior to healing with a duration of 336 hours (14 days x 24 hours).	Hodges-Lehmann estimation methods; Wilcoxon rank sum test to compare groups
		Sensitivity Analysis	Subjects who drop out prior to healing will be considered censored.	Kaplan-Meier estimation methods; Log-rank test to compare groups
	EE	Main Analysis	No imputation required since these are complete cases.	Hodges-Lehmann estimation methods; Wilcoxon rank sum test to compare groups
Prevention of Progression	MITT/EE	Main Analysis	No imputation	chi-square or Fisher's exact test to compare groups
Area	MITT/EE	Main Analysis	No imputation	t-test or Wilcoxon rank sum test to compare groups
Pain Severity	MITT/EE	Main Analysis	No imputation	Cochran-Mantel-Haenszel test to compare groups

\*All analyses in this matrix will be completed for all subjects in the specified Analysis Population, then the analyses will be stratified for subjects treated at Stage 1 and those treated at Stage 2.

### 7.13.6 Pooling of Centers

This is a multi-center study planned at multiple investigational sites. As all sites will be functioning under the same protocol, it is assumed that no substantial differences between sites will be evidenced in the data and the data from all centers will be pooled together for analyses. However, formal statistical assessment of these assumptions will be explored. In order to assess pooling of data from multiple centers or whether there are differences among centers in treatment effects, a Cox proportional hazards model analysis of the duration of herpetic episode will also be performed for the primary duration endpoint and for both the MITT and EE Populations. The model will include terms for treatment, center, and treatment by center interaction. A test will be performed to test for the significance of the interaction. This test will be conducted at the 0.10 level of significance. If the interaction is found to be significant, estimates of treatment effect will be provided by center, as well as overall.

## 8 Handling of Missing Data

All missing data will be queried. Missing efficacy data on duration endpoints for subjects in the MITT Population which are not retrievable through queries will be handled using imputation of 336 days. Other missing data, including missing safety data, will not be imputed.

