## 10.7 Efficacy Analysis

The efficacy analysis will be performed on both the MITT and the efficacy evaluable populations. For all duration endpoints the following matrix will be used for analyses:

Population	Analysis	Description	Methods
MITT	Main Analysis	Impute duration for subjects who drop out prior to healing with a duration of 336 hours (14 days x 24 hours).	Hodges-Lehmann estimation methods; Wilcoxon rank sum test to compare arms
	Sensitivity Analysis	Subjects who drop out prior to healing will be considered censored.	Kaplan-Meier estimation methods; Log-rank test to compare arms
EE	Main Analysis	No imputation required since these are complete cases.	Hodges-Lehmann estimation methods; Wilcoxon rank sum test to compare arms

For all endpoints on the occurrence of prevention of progression, counts and percentages will be summarized, and chi-square tests, or Fisher's exact test will be used to compare arms, as appropriate. Fisher's exact tests will be used if any of the expected cell counts in the Rx C crosstabulations are less than 5.

For size endpoints, means, medians, standard deviations and ranges will be summarized. T-tests will be used to compare arms if the sizes are approximately normally distributed, or Wilcoxon rank sum tests will be used if the sizes are markedly non-normally distributed.

For the severity endpoints, counts and percentages will be summarized, and Cochran-Mantel-Haenszel tests will be used to compare the arms.

In order to assess whether there are differences among centers in treatment effects, a Cox proportional hazards model analysis of the duration of herpetic episode will also be performed for the primary duration endpoint and for both the MITT and EE populations. The model will include terms for treatment, center, and treatment by center interaction. A test will be performed to test for the significance of the interaction. This test will be conducted at the 0.10 level of significance. If the interaction is found to be significant, estimates of treatment effect will be provided by center, as well as overall.

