### 7.1.2 Modified Intent-to-Treat (MITT) Population

All subjects who have been entered into the Treatment Phase of the study will be included in the modified intent-to-treat (MITT) Population. It is considered a “modified” intent to treat population in that it does not include all randomized subjects but includes only those randomized subjects who access their treatment, i.e., are told to open their kit. A subject will be included in a treatment group for analysis based upon the treatment to which he or she has been assigned; imputation on the primary endpoint only is planned for the MITT Population – see section 7.13. The MITT Population will be used as the primary analysis population and for all efficacy analyses.

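### SAP 8 imputes 336 days where the three other places say 336 hours, and no sound rule covers lesions that have not reached the endpoint stage by Visit Day 14

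*SAP*

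**What the plan says.** **Imputed value.** SAP 8 states that missing MITT durations "which are not retrievable through queries will be handled using imputation of 336 days". Three other places give a value, and all three give hours. The matrix in Protocol 10.7 reads "Impute duration for subjects who drop out prior to healing with a duration of 336 hours (14 days x 24 hours"; SAP 7.13.1 says that these subjects' durations "will be imputed with a duration of 336 hours (14 days x 24 hours"; the matrix in SAP 7.13.5 repeats the protocol. SAP 6.1.4 measures duration in hours, and clinic visits stop at Stage 7 or at 14 days.

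**Scope.** SAP 7.1.2 says "imputation on the primary endpoint only is planned for the MITT Population" and refers the reader to section 7.13. There, SAP 7.13.1 says "Imputation will only be used for analyses of duration endpoints and only in the MITT Population", which covers every duration endpoint.

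**EE population.** Protocol 10.3.3 and SAP 7.1.3 admit subjects who completed treatment and were followed until healing or for 14 days. Both restrict EE to observed values. SAP 7.13.1 then says "For analysis of duration in the EE Population, no imputation is required since these are complete cases", and the matrices in Protocol 10.7 and SAP 7.13.5 agree.

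**Pain.** Protocol 10.7.7 and SAP 6.1.4 censor pain still present at 14 days. The main analysis of every duration endpoint is a Wilcoxon rank sum test with a Hodges-Lehmann estimate. Only the MITT sensitivity analysis uses Kaplan-Meier and log-rank.

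**The concern.** The section a programmer would consult for missing data carries a value 24 times that of the other three places. SAP 7.2 asks for the mean, SD, minimum and maximum of continuous variables, so the slip could reach the tables.

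Correcting the unit does not finish the job. A subject who attends through Visit Day 14 without reaching the endpoint stage has not dropped out, so the 336-hour rule does not name that subject. In EE the same subject qualifies but has no duration and falls out of the rank test without comment. These are the longest lesions, so which arm they come from matters.

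Two lesser gaps sit beside this: the scope statement in SAP 7.1.2 contradicts SAP 7.13.1 and SAP 8, and a censored pain duration has no defined value in the main rank test. With these left open, two programmers could produce different MITT means and different EE results, and a choice made after unblinding could look data-driven.

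**Working it through.** **1. The plan's own figure.** 14 × 24 = 336 h, as three places state. With Visit Day 1 at 0 to 24 h after entry and visits at the same time each day, Visit Day 14 falls at 312 to 336 h (13 × 24 = 312). SAP 8 as written gives 336 × 24 = 8,064 h, or 48 weeks.

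**2. Effect of the unit on summaries.** Take 75 × 0.75 ≈ 56 classical lesions per arm (25% aborted, from the sample size section; the same section says about 60). Each imputed subject adds (8,064 − 336)/56 = 138 h to the arm mean. Assume 53 observed durations with mean 200 h and SD 77 h, capped at 336 h, plus 3 imputed. The SD of 77 h is back-solved as 41/(1.919 × √(1/32 + 1/22)) from the earlier study's 41 h and p = 0.055, treating 32 and 22 as that comparison's sizes.

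| Imputed value | Arm mean | Arm SD |
|---|---|---|
| 336 h | 206.3 h | 78.9 h |
| 8,064 h | 620.3 h | 1,788.5 h |

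The median is about 205 h either way.

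**3. Effect of the unit on the rank test.** If every observed duration is below 336 h, imputed values hold the top tied rank under either unit and p is identical. Differences need observed values at or above 336 h. In 4,000 simulated trials per setting (placebo mean 200 h, active 153 h, SD 77 h):

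| Setting (imputed placebo/active) | Mean p shift | Largest | Crossing 0.05 |
|---|---|---|---|
| All observed below 336 h | 0 | 0 | 0 |
| Capped at 336 h, 3/3 | 0.0009 | 0.035 | 0.2% |
| Capped at 336 h, 1/5 | 0.0044 | 0.054 | 1.35% |
| Observed up to 345 h, 3/3 | 0.0017 | 0.043 | 0.7% |

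The Hodges-Lehmann estimate moves by 0.6 h on average (capped, 3/3) and 1.3 h (capped, 5/1). With gamma durations and 2% to 15% dropout the average shift is 0.4 to 1.1 h, with a single-trial maximum of 10.2 h.

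**4. Which rule reaches whom.**

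| Subject | MITT rank test | EE rank test |
|---|---|---|
| Leaves before healing | 336 h (Protocol 10.7, SAP 7.13.1, 7.13.5); 336 days (SAP 8) | Not in EE |
| Followed to Visit Day 14, endpoint stage not reached | Only SAP 8, if this counts as missing | In EE, no value |
| Pain unresolved at 14 days | Censored, which the test cannot use | Same |

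For the primary endpoint the ending stage is Stage 6, or Stage 7 if Stage 6 is never observed. For complete healing it is Stage 7.

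**5. Size of the EE gap.** Effects in SD units: z for p = 0.0276 is 2.203, and 2.203 × √(1/32 + 1/22) = 0.61 if all 32 and 22 subjects were analysed. With 25% aborted, 2.203 × √(1/24 + 1/16.5) = 0.70. Both come from Stage 1 starters and this trial admits Stage 2, so 0.40 is added as an assumed lower value. Normal durations differing by a shift, 56 per arm, 20,000 replicates; power if unhealed lesions are dropped versus assigned 336 h:

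| Placebo unhealed | Effect 0.61 | Effect 0.70 | Effect 0.40 |
|---|---|---|---|
| 1% | 0.865 vs 0.877 | 0.939 vs 0.946 | 0.509 vs 0.522 |
| 2% | 0.858 vs 0.879 | 0.932 vs 0.944 | 0.501 vs 0.532 |
| 5% | 0.826 vs 0.877 | 0.915 vs 0.947 | 0.458 vs 0.531 |
| 10% | 0.767 vs 0.876 | 0.874 vs 0.946 | 0.404 vs 0.530 |

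At 0.61 the Hodges-Lehmann estimate shrinks by about 3%, 4%, 10% and 17%. With 60 per arm the losses at 1%, 5% and 10% are 1.0, 5.1 and 9.9 points. With no true effect and 5% unhealed, dropping gave a type I error of 0.049.

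**The case against.** The unit conflict resolves itself: the endpoint is in hours, three places print the multiplication, follow-up stops at 14 days, and SAP 9 plans no departure from the protocol. A competent programmer would use hours. That stands. A reader might infer that the primary result is at risk; step 3 shows that it is not.

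EE is supportive, since MITT is the primary population. The unhealed rate is not in the documents. Nor is the EE size: EE requires completed treatment, while Protocol 7.2.4 has subjects stop remaining treatment at Stage 4, so the number of classical lesions that qualify is unknown. At 40 per arm (effect 0.61, 5% unhealed) power is 67% against 73%: a similar loss from a lower start. This also stands.

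A reader might infer that EE is always biased toward no difference. The direction depends on the model. In a second simulation (gamma durations, true difference 41 h, 60 per arm, unhealed status unrelated to the other durations), one unhealed per arm gave power 0.90 dropped and 0.89 assigned. With 6 on placebo and 3 on active, dropping gave −42.1 h, close to the truth, and assigning gave −47.3 h (power 0.87 against 0.92).

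A reader might also infer a false-positive risk, or that any lesion short of normal skin at Day 14 lacks a primary value. The first is not seen in step 5. The second is wrong, because Stage 6 ends the primary endpoint.

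**Conclusion.** The point holds and should be settled before unblinding, but it does not threaten the primary p-value. SAP 8 is wrong as written: the effect on the primary Wilcoxon test is nil or very small, while the effect on MITT means, SDs and maxima is gross.

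The substantive gap is the subject followed to Visit Day 14 without reaching the endpoint stage. In MITT only the faulty sentence could cover that subject. In EE nothing does, and describing EE as complete cases is incorrect by its own definition. If such lesions are more frequent on placebo and durations follow a common shifted distribution, EE is pulled toward no difference, by about 1, 5 and 11 power points at 1%, 5% and 10% of placebo unhealed (effect 0.61, 56 per arm). The rates, the effect, the distribution and the EE size are all assumptions; at 1% to 2% unhealed the loss is 1 to 3 points across the three effects. The scope wording in SAP 7.1.2 and the pain rule are minor.

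**What to change.** 1. **SAP 8:** change '336 days' to '336 hours', and refer to SAP 7.13.1 for who receives the value.
2. **SAP 7.1.2:** change the scope from the primary endpoint only to duration endpoints only.
3. **MITT (Protocol 10.7, SAP 7.13.1, SAP 7.13.5):** for durations measured from the start of treatment, extend the 336-hour rule to subjects in the endpoint's analysis set who are followed to Visit Day 14 without reaching the endpoint stage, using the last assessment time if that is later. Classical-lesion endpoints take classical lesions only, so that an unhealed aborted lesion does not acquire a classical-lesion duration. Censor these subjects at the last assessment in the Kaplan-Meier analysis. Do not replace observed durations.
4. **EE (same sections):** delete the complete-cases description, state that these lesions have no EE duration under the no-imputation rule, and report their number per arm and endpoint. Optionally add a supplementary EE rank analysis that gives them the highest tied rank.
5. **Pain and hard scab (Protocol 10.7.6 and 10.7.7, SAP 6.1.4):** state that the pain censoring sentence applies to the Kaplan-Meier and log-rank analysis. In the MITT rank test give unresolved subjects the highest tied rank. These clocks start at first pain and at Stage 5 onset, so a flat value counted from first treatment does not fit.

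The cost is a set of wording edits and a little programming before unblinding, with no new data. EE is then openly shown not to consist of complete cases.

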## **9 Changes from the Protocol**

No changes in the analyses described in the original protocol or subsequent amendments are planned. If changes are made prior to unblinding, this document may be amended and such changes will be described. Changes made after unblinding will be noted in the clinical study report.

## 10 Tables

Disposition

Demographics – Safety

Demographics – MITT

Demographics – EE

Medical History – Safety

Medical History – MITT

Medical History – EE

Efficacy – Duration Endpoints – MITT

Efficacy – Duration Endpoints – EE

Efficacy – Prevention of Progression – MITT

Efficacy – Prevention of Progression – EE

Efficacy – Area Endpoints – MITT

Efficacy – Area Endpoints – EE

Efficacy – Pain Severity – MITT

Efficacy – Pain Severity – EE

Summary of Subjects with TEAEs – Safety

Occurrence of TEAEs by SOC and PT – Safety

Occurrence of TEAEs Related to Treatment by SOC and PT – Safety

Occurrence of Severe TEAEs by SOC and PT – Safety

Occurrence of Serious TEAEs by SOC and PT – Safety
